7.4 RANDOMIZATION AND BLINDING.....	15
7.5 METHODS AND INTERVENTION	16
7.6 PATIENT-REPORTED OUTCOMES	18
7.7 CONCOMITANT AND SUPPORTIVE THERAPY.....	19
7.8 DISCONTINUATION AND WITHDRAWAL OF SUBJECTS	19
7.9 ADDITIONAL INFORMATION	20
8. STUDY CALENDAR	21
9. ADVERSE EVENTS.....	22
9.1 GENERAL	22
9.2 REPORTING PROCEDURES	22
10. MEASUREMENT OF EFFECT.....	23
11. DATA AND SAFETY MONITORING.....	23
11.1 DATA MANAGEMENT	23
11.2 MONITORING.....	23
12. ADMINISTRATIVE PROCEDURES	24
12.1 PROTOCOL AMENDMENTS	24
12.2 INFORMED CONSENT	24
12.3 ETHICS AND GOOD CLINICAL PRACTICE	24
12.4 REGULATORY AUTHORITIES.....	24

13. STATISTICAL CONSIDERATIONS.....	25
13.1 OVERALL.....	25
13.2 SAMPLE SIZE AND ACCRUAL.....	25
13.3 ANALYSIS PLAN	26
13.4 REPORTING AND EXCLUSIONS	27
APPENDICES.....	27
APPENDIX A: ECOG PERFORMANCE STATUS SCALE	28
APPENDIX B: MODIFIED BRIEF PAIN INVENTORY.....	29
APPENDIX C: EUROPEAN ORGANIZATION FOR RESEARCH AND TREATMENT OF CANCER QUALITY OF LIFE CANCER CHEMOTHERAPY INDUCED PERIPHERAL NEUROPATHY-20 INSTRUMENT (CIPN-20)	31
APPENDIX D: CONCOMITANT PAIN MEDICATIONS/PARTICIPANT DIARY.....	32
REFERENCES	33

1. Summary

Scrambler Therapy is a personalized neuro-cutaneous method of pain relief that has been effective in reducing chronic neuropathic pain in multiple uncontrolled trials. Treatment is given with common EKG skin electrodes placed above and below the pain, and the Scrambler Therapy machine directs electrical signals across the field to simulate non-pain information. The treatment is non-invasive and takes 30 minutes a day for 10 days. To date, the pain relief has been straightforward and dramatic.

[figure not shown]
Chemotherapy induced peripheral neuropathy (CIPN) is a major and often dose-limiting side effect of antineoplastic agents. The incidence of chemotherapy-induced neurotoxicity ranges from 0 to 70% (commonly 30-40%) of patients receiving chemotherapy, related to the timing and cumulative dose. Pain is the most common symptom, usually described as a burning, stinging dysesthesia. There is no standard effective therapy for CIPN pain.

We propose a straightforward randomized controlled trial of actual Scrambler Therapy versus sham therapy (electrodes placed on the back, which does not cause pain relief but was perceived as active treatment in our pilot trials).

The primary endpoint is patient reported change in pain from day 0 to day 28, on a numeric scale of 0-10 (question #3 of the Modified Brief Pain Inventory, Appendix B). Secondary endpoints will include changes in the complete Brief Pain Inventory, the CIPN EORTC Q-20 scale, and changes in pain drug use. With 30 patients and a one-sided type I error rate of 10%, we have 87% power to detect a 50% reduction in pain observed in single arm trials and a 10% reduction in pain with sham treatment, in patients with a starting pain score of ≥ 4 .

Subjects enter the study and get scrambler therapy or placebo for 10 sessions, usually as weekdays, for 2 weeks. Then, they are followed without any protocol treatment until Day 28 when the primary endpoint is assessed. After the primary assessment is done the groups are “un-blinded” and informed of their study treatment, real or sham. Those in the sham group with scores ≥ 4 will be offered the standard 10 scrambler sessions. All patients are followed for a total of 3 months.

2. Schema

3. Objectives

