13.2 Sample Size and Accrual

We are anticipating that the starting pain score will be 4-6 based on VCU, Italian, and Mayo Clinic data. We are anticipating that the reduction in CIPN pain score will be over 50% based on the VCU, Italian, and Mayo Clinic data. We anticipate a possible 10% reduction in pain scores over 30 days based on the randomized trial data for placebo compared to gabapentin and other drugs.

The primary objective of this study is to determine if patients randomized to the Scrambler therapy have a larger reduction in pain scores than those randomized to the placebo, or sham, treatment. Power calculations were performed using a simulation approach. Pain scores were simulated using a bivariate normal distribution with a mean (SD) of 4 (2) at baseline for both groups, with means ranging from 2.8 to 3.6 (30% to 10% decrease) for the control group post-treatment and mean of 2 (50% decrease) for the Scrambler group post-treatment. Post-treatment scores for both treatment arms were assumed to have a SD = 1.5. Based on previous data, a value of 0.3 was assumed for the within-patient correlation between pre- and post-treatment scores.

Any patient with 1) a simulated pain score at baseline less than 4, or 2) a simulated pain score less than 0 post-treatment, or 3) a simulated pain score greater than 10 at either time point, was replaced until all criteria were met, to reflect the actual scores we will see. Simulated scores were then rounded to the nearest integer to also reflect the nature of the scale. The change in pain score was calculated for each patient, and differences were compared between groups with a two-sample t test. Power was defined as the proportion of simulations that yielded a one-sided p value for the t test < 0.10 . 1000 simulations for each scenario were performed. The table below shows sample sizes and resulting power for the differences between treatment arms.

Total N	Power	Percent Decrease in Treatment Arm	Percent Decrease in Control Arm
30	87.3%	50%	10%
60	86.6%	50%	20%
90	77.6%	50%	30%

To detect the proposed effect size, 30 patients total, 15 on Scrambler therapy and 15 on the sham arm, will yield 87.3% power with a 1-sided type I error rate of 10%.

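### The Section 13.2 simulation, run as described with many replicates, gives about 85% power for 30 patients, not the stated 87%

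*Combined protocol and SAP*

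**What the plan says.** Section 1 (Summary) supports the sample size with the statement that "we have 87% power to detect a 50% reduction in pain observed in single arm trials", set against a 10% reduction with sham.

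Section 13.2 gives the method.
- **Baseline:** "Pain scores were simulated using a bivariate normal distribution with a mean (SD) of 4 (2) at baseline for both groups".
- **Post-treatment mean, sham:** "with means ranging from 2.8 to 3.6 (30% to 10% decrease) for the control group post-treatment".
- **Post-treatment mean, Scrambler:** "mean of 2 (50% decrease) for the Scrambler group post-treatment". The post-treatment SD is 1.5 in both arms and the pre/post correlation is 0.3.
- **Replacement:** a simulated patient is replaced if the baseline score is below 4, the post-treatment score is below 0, or either score is above 10.
- **Rounding and test:** scores are rounded to integers after replacement, and the change scores are compared with a two-sample t test.
- **Power:** "Power was defined as the proportion of simulations that yielded a one-sided p value for the t test < 0.10".
- **Replicates:** "1000 simulations for each scenario were performed".

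The table has three rows: 87.3% for N=30 with a 10% control decrease, 86.6% for N=60 with 20%, and 77.6% for N=90 with 30%. The closing sentence names "30 patients total, 15 on Scrambler therapy and 15 on the sham arm" and attaches the 87.3% figure, at a one-sided 10% error rate, to that size. No Monte Carlo error, seed or code is given.

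**The concern.** The power figure is the quantitative argument for 30 patients, and it appears in two places, once to a decimal. Because 13.2 specifies the algorithm completely, the figure can be checked without any outside assumption, and it does not come back. At the planned effect, the chance of missing a true difference is about 15.0% rather than 12.7%.

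There is a related gap in the table. N rises together with the sham response, so the size actually chosen is shown only at the most favourable of the three sham inputs. Section 13.3.1 says the study is meant to inform larger trials. Anyone reading a null result for that purpose would want to know what 30 patients deliver at the other two inputs.

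**Working it through.** **Inputs (all from 13.2).** Baseline mean 4, SD 2. Post-treatment mean 2 for Scrambler. For sham the mean is 4 × (1 − 0.10) = 3.6, 4 × (1 − 0.20) = 3.2 or 4 × (1 − 0.30) = 2.8. Post-treatment SD 1.5; correlation 0.3, so the covariance is 0.3 × 2 × 1.5 = 0.9. Equal arms of 15, 30 or 45. One-sided α = 0.10. The percentage labels are the plan's own and refer to the means before replacement.

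**Algorithm, in the order of the text.** Draw the pair; redraw the patient if baseline < 4, post < 0 or either > 10; round both scores; take the change; apply a pooled two-sample t test; count the proportion with one-sided p < 0.10.

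**Results as written**

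| Total N | Sham mean | Stated | Recomputed |
|---|---|---|---|
| 30 | 3.6 | 87.3% | 85.0% (2,000,000 replicates, Monte Carlo SE 0.03 points) |
| 60 | 3.2 | 86.6% | 87.8% |
| 90 | 2.8 | 77.6% | 75.2% |
| 30 | 3.2 | not shown | about 67% |
| 30 | 2.8 | not shown | about 44% |

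A Welch test instead of the pooled test also gives 85.0% for N=30.

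**Could 1,000 replicates explain the gap?** The standard error of a simulated power is √[p(1 − p)/1000].
- N=30: √(0.850 × 0.150/1000) = 0.0113. The stated value is (0.873 − 0.850)/0.0113 ≈ 2.0 SE high.
- N=60: √(0.878 × 0.122/1000) = 0.0104, so (0.866 − 0.878)/0.0104 ≈ −1.15 SE.
- N=90: √(0.752 × 0.248/1000) = 0.0137, so (0.776 − 0.752)/0.0137 ≈ 1.8 SE.

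If true power is 85.0%, the probability of at least 873 successes in 1,000 is about 0.022. The exact 95% interval for 873/1000 is 85.1% to 89.3%, which only just misses 85.0%. Jointly, 2.0² + 1.15² + 1.77² ≈ 8.5 on 3 df, p about 0.04. Chance is possible but not comfortable.

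**Could the code differ from the text?** Two small departures, each run for all three rows:

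| Variant | N=30 | N=60 | N=90 | SEs from stated |
|---|---|---|---|---|
| Round before replacement | 85.9% | 88.8% | 76.9% | 1.28, −2.21, 0.53 |
| No rounding | 87.1% | 89.4% | 77.5% | 0.21, −2.88, 0.12 |

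Joint fit: 1.28² + 2.21² + 0.53² ≈ 6.8 (p about 0.08) with rounding first, and 0.21² + 2.88² + 0.12² ≈ 8.4 (p about 0.04) without rounding. Either variant moves N=30 towards the stated figure, but neither fits the N=60 row well. No variant tried matches all three rows closely.

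**The case against.** The best defence is that nothing was misreported. The plan discloses 1,000 simulations and defines power as the proportion that succeed, so 87.3% is 873/1000, and any reader can work out its standard error. The inputs are round planning values, and a 2-point shift is small beside their uncertainty. Section 13.3.1 describes the trial as closer to an early randomized phase 2 study. Power remains above 80% at the planned effect. All of this stands, and it is why the point is minor. It does not make 87% the right figure to keep in two places when the described algorithm gives 85%.

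The plan is also open that 87% belongs to a 10% sham reduction, and it bases that value on placebo results in earlier randomized trials. Showing N=30 at the other two inputs therefore improves the presentation; it does not correct an error.

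Two stronger readings are tempting. A reader might conclude that 87% is simply a lucky draw. The documents do not support that: such a draw has only about a 2% chance under the text as written, and a change in rounding would also raise the N=30 figure. A reader might also make much of N=30 being printed above N=60 when the recomputation puts N=60 higher. The printed difference is 87.3 − 86.6 = 0.7 points, less than one Monte Carlo SE, the rows differ in both N and sham response, and no decision rests on their order.

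**Conclusion.** The concern holds as a small correction to a stated figure. The algorithm in 13.2, taken literally, gives about 85% for N=30, which is 2.3 points below 13.2 and about 2 points below the Summary. The N=60 row is about 1.2 points too low and the N=90 row about 2.4 points too high. This rests on the text being the algorithm that was coded. If rounding came before replacement or was left out, the N=30 figure would be about 86% or 87%. The cause, chance or coding, cannot be settled from the documents.

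A reader might infer that the trial is underpowered, either from the drop to 85% or from the 67% and 44% entries. The documents do not support that inference. The planned effect assumes a 10% sham reduction, and at that input power is still above 80%. The lower figures show how power depends on the sham response; they do not show that the planning assumption is wrong.

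**What to change.** 1. Confirm that the simulation code matches 13.2, in particular that rounding was done, and after replacement.
2. Re-run all scenarios with at least 100,000 replicates and state the replicate count and Monte Carlo error.
3. Restate the power as whole percentages in Section 1 and in the table and closing sentence of 13.2: about 85%, 88% and 75% if the text is the algorithm. If the code differs, correct the description and report what that code gives.
4. Add N=30 at all three sham inputs to the table: about 85%, 67% and 44% under the text as written.

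The cost is minutes of computing and a wording change. No patients are added, and the test and decision rule stay as they are. The only downside is a slightly less favourable stated power.

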3.1 Primary

3.1.1 To determine the change in pain from day 0 to day 28 with scrambler therapy in patients with chemotherapy induced peripheral neuropathy and pain (CIPN). This endpoint also serves to get preliminary information for planning future, larger, phase III studies.

The primary measurement tool for pain will be the Brief Pain Inventory (BPI) (modified specifically for CIPN by the originator, [name], and used with permission) which gives information on Pain Now, Worst, Least and Average Pain, and Interference with Normal Activity.

3.2 Secondary

3.2.1 The secondary endpoints will include changes in the complete Brief Pain Inventory, the CIPN EORTC Q-20 scale, and changes in pain drug use.

3.2.2 The primary measurement tools used to determine if MC-5A Calmare therapy will improve endpoints include the following: neuropathy (European Organization for Research and Treatment of Cancer Quality of Life Cancer Chemotherapy Induced Peripheral Neuropathy-20 Instrument (CIPN-20)); opiate use (morphine oral equivalent daily dose, MOED) and other drug (anti-depressant, anti-convulsant) use. We will also study the duration of the effect.

4. Hypotheses

4.1 Primary

- Scrambler Therapy will improve pain related to chemotherapy-induced neuropathy significantly more than sham therapy at day 28.

4.2 Secondary

- Scrambler Therapy will result in significant improvements in the total CIPN modified Brief Pain Inventory score and the motor and sensory subscales of the CIPN 20 compared to sham therapy.
- Pain medication and morphine oral equivalent dose (MOED) daily amounts will decrease by at least 20% more from the start of treatment Day 1 (pre) to Day 30 days (post), in the group receiving scrambler therapy versus those who received sham therapy.

5. Background and Rationale

5.1 Neuropathy due to chemotherapy agents (CIPN)

CIPN is a major and often dose-limiting side effect of antineoplastic agents¹ including the taxanes (paclitaxel and docetaxel), platinums (carboplatin, cis-platinum, and oxaliplatin), vinca alkaloids (vincristine, vinblastine, and vinorelbine), proteosome inhibitors (bortezomib²), immunomodulating drugs such as lenalidomid³, and epithelones such as ixabepilone⁴. The incidence of chemotherapy-induced neurotoxicity ranges from 0 to 70% (commonly 30-40%) of patients receiving chemotherapy, related to the timing and cumulative dose.⁵ Unlike chronic diabetic nerve damage, it is not caused by nutritional starvation but rapid damage to microtubules of the nerves.⁶ Pain is the most common symptom, usually described as a burning, stinging dysesthesia. However, many patients also complain of numbness and being unable to do activities of daily living because they cannot feel their fingertips or toes. This numbness is often progressive over the day such that sensation is lost by the end of the day.

There is no standard effective therapy for CIPN pain. Tricyclic antidepressants (TCAs) do not work for CIPN and have significant adverse effects. Amitriptyline⁷ and Nortriptyline⁸ were no better than placebo in randomized trials. Lamotrigine had no effect on CIPN in a randomized placebo controlled trial.⁹ Gabapentin does not work for CIPN when compared to placebo.¹⁰ Magnesium and calcium infusion does not prevent oxaliplatin-induced neuropathy¹¹. Vitamin E may be helpful but may also protect the cancer; use is not suggested until larger randomized trials are completed. Acetyl-L-carnitine has been reported to reduce established CIPN in one small series¹² but the investigators caution against its use until safety and efficacy can be confirmed in larger randomized trials.¹³ Venlafaxine¹⁴ reduced the incidence or prevented oxaliplatin-CIPN from 76% to 35% but has only been tested in oxaliplatin, a drug not used in breast cancer treatment, and has not been tested as a treatment drug. Topical baclofen-amitriptyline-ketamine (BAK) gel reduced CIPN-sensory symptoms compared to placebo¹⁵, but incompletely and not in the feet – where the symptom is most common. Duloxetine (Cymbalta) is the only drug shown in a randomized trial to reduce CIPN pain scores¹⁶, but only from 6 to 5 over 6 weeks, caused side effects, and only worked for oxaliplatin neuropathy -- not for taxane-induced CIPN which is far more common in women with breast cancer.

Acupuncture reduced CIPN pain scores in small, non-randomized series of 5¹⁷ and 18¹⁸ cancer patients. In one larger trial, acupuncture relieved CIPN from paclitaxel and oxaliplatin more effectively than drug treatment with Vitamin B12 injections, 67% vs. 40%¹⁹. In one small trial, nerve conduction studies showed improvement after acupuncture: 5 of 6 patients improved clinically, correlated with improvements in mean nerve conduction velocity (NCV) (m/s) and mean amplitude (μ V) ($p=0.03$)²⁰ suggesting that CIPN-damaged nerves can indeed repair. However, none of these trials had any standard control or sham/placebo group.

5.2 Direct Nerve Stimulation in Chronic Pain Relief

There is much clinical experience that CIPN and other chronic pain syndromes can be helped by direct nerve stimulation²¹. The hypothesized mechanisms by which direct nerve stimulation reduces pain include reducing impulses from the damaged nerve, raising the “gate” threshold for pain at the spinal cord, reducing “wind up” (central sensitization of the spinal cord and brain that amplifies the abnormal feelings), and reducing psychological maladaptation to pain²². Spinal

cord stimulation has been successful in small, non-randomized series^{23 24} for chronic pain from reflex sympathetic dystrophy²⁵ and post-herpetic neuropathy²⁶ but has not been assessed in CIPN. Peripheral nerve stimulation^{27 28} is growing in use but there are no controlled trials to date. Not all therapies work, however, as the published data show that trans-cutaneous electrical nerve stimulation (TENS) is not useful in cancer pain²⁹, and TENS has not been evaluated in CIPN.³⁰

5.3 Scrambler Therapy

5.3.1 Rationale for nerve-based treatments like Scrambler Therapy

Scrambler Therapy is a novel treatment whose efficacy for CIPN is supported by clinical experience and pilot trials, but for which rigorously designed, sham-controlled trials do not exist. The goal of the device is to provide “non-pain” information to the cutaneous nerves to block the effect of pain information

The device is a cutaneous electrical stimulator that uses C fiber stimulation to transmit patterns of waveforms simulating 16 different action potentials to reset the brain to perceive non-pain from areas previously interpreted as painful. Proprietary software designs the patient-specific cutaneous electro-stimulation to reduce the abnormal pain intensity. The device consists of a multiprocessor apparatus able to simulate 5 artificial neurons by the application of surface electrodes on skin pain areas. The device synthesizes 16 different types of nerve action potentials similar to the endogenous kinds, strings them into sequences, and directly stimulates the peripheral nerves.

The scientific rationale for the observed pain relief is shown in Figure 1. The relationship between clinical pain relief and the hypothesized active principle requires further validation and independent studies, but we have some hypotheses. First, it is not just C fibre excitation; electrical C fibre excitation without information should also produce pain, whereas Calmare therapy produces pain

relief. Second, Calmare therapy is not just producing widespread paraesthesia. The patient feels the effect of stimulation only in the painful area under the electrode contact-area. Immediately after the treatment, no paresthesia or anesthesia is noted. Furthermore, the intensity of stimulation current is very low, and peaks never exceed 5.5 mA, which is likely too low to produce analgesia. Fourth, the sensation perceived by the patient (electrical current, pressure, flow, or other “bee sting” sensations under the electrodes) suggests that non-pain stimuli are being felt, not just analgesia numbing sensation. Another aspect of the hypothesized pain relief is

[figure not shown]

Figure 1: Mechanisms of pain and Calmare Treatment

that analgesia occurs within minutes or hours and slowly accumulates over several days, suggesting nerve remodulation or remodelling.

The exact mechanism by which similar types of nerve stimulation reduce pain is complex and not completely understood. Regardless of the mechanism, the therapy appears to work or at least warrant further testing.

5.3.2 Preliminary data on Scrambler therapy

The Scrambler Therapy device appears to work on pain based on results from multiple trials. In the first trial, 11 cancer patients (3 pancreas, 4 colon, 4 gastric) suffering from drug resistant visceral pain were studied during their first ten treatment sessions.³¹ Pain was quickly and markedly reduced and maintained until death. Nine of 11 stopped pain drugs within the first 5 applications. In the second trial, 226 patients with neuropathic pain including failed back surgery, brachial plexus neuropathy, and others were treated.³² 80% of patients responded with > 50% pain relief, 10% responded with pain relief from 25% to 49%, and only 10% had no response (P<0.0001).

Based on these results the FDA approved Scrambler therapy for cancer pain treatment February 25, 2009. In clinical practice, over 4000 patients have been treated worldwide with no reported side effects except occasional transient worsening of pain. In addition, at least one patient had some temporary bruising under the sites of the electrodes.

In the first US trial, Smith et al³³ studied 16 typical patients (median age 56, usual chemotherapy drugs) with refractory CIPN and pain scores over 6. Each patient was treated for 10 sessions of 60 minutes each, Monday through Friday. The electrodes were applied in the areas of the pain, as shown in Figure 2. The results are shown in Figure 3. *The average pain reduction was 59%, similar to direct spinal cord stimulation.* The effect on some patients was dramatic, with 4 people having no pain and several resumed normal activity. The effect was persistent, lasting weeks to months in most patients, with successful retreatment if needed.

Mayo Clinic investigators have now replicated these results in a pilot trial, with a 47% reduction in CIPN pain.³⁴ The 10 day time period is too short for any

Figure 2:MC5-A Scrambler Therapy for CIPN, application of electrodes for

[figure not shown]

Figure 3: Scrambler Therapy and CIPN Results, Smith et al.

[figure not shown]
[figure not shown]

Figure 5: Scrambler Therapy and Neuropathic Pain, Ricci et al.

natural reduction in CIPN, making this unlikely to be natural resolution. (Figure 4)

Ricci et al treated 47 cancer pain patients (many types of pain, not just CIPN) with Scrambler therapy. Pain intensity decreased by 74% from 4.7 (SD 2.9) at baseline to 2.5 (SD 2.3) at the end of the second week of treatment and 2.6 (SD 2.6) at one month. (Figure 5) Nearly all patients found it satisfactory or very satisfactory and would continue using it.³⁵

In a pilot randomized trial³⁶, 52 patients with chronic neuropathic pain (spinal cord stenosis, failed back syndrome, post-herpetic neuropathy) were randomized to Scrambler therapy or treatment by the same expert group following standard pharmacology guidelines³⁷. The patients had post-surgical failed back, post herpetic, or spinal stenosis neuropathy. These results are shown in Figure 6. The mean pain intensity score at outset was 8.1. At one month, the Scrambler therapy group had a 91% decrease in pain to 0.7 points, and the standard therapy group had a 28% reduced pain score, which was maintained for 3 months. Pain drug consumption decreased by 72% in the Scrambler therapy group, including opiates, anti-depressants, and anti-convulsants. Allodynia, or pain on normal touching of the skin, was reduced in the Scrambler therapy patients from 77% to 15% at 3 months. All differences were both clinically and statistically significant.

Other small series show a >50 % reduction in refractory post –herpetic pain³⁸ and cancer pain³⁹.

In a large series of complicated pain patients, including spinal pain, neuralgia, chronic regional pain syndrome, and multisite pain, D'Amato and colleagues reported a significant reduction in pain scores across all diagnostic groups⁴⁰. (Figure 7)

In a recent trial, Pachman et al treated 13 patients with refractory low back pain at the Mayo Clinic. Mean average daily pain scores decreased by 54% from baseline to day 10 of treatment. Median weekly pain scores decreased by 70% after 10 weeks of follow up, as shown in Figure 8. Patients also reported improvements in quality of life that persisted through 10 weeks of follow up. The data suggest that scrambler therapy effectively treats chronic low back pain, supporting the conduct of a placebo-controlled, randomized trial. (Pachman D, et al. submitted for publication)

[figure not shown]

Figure 6: Scrambler Therapy (top) compared to best medical management

[figure not shown]

Figure 7: Reduction in Chronic Pain with Scrambler Therapy

[figure not shown]

Figure 8: Pilot trial of Scrambler therapy for low back pain

In the most recent trial, Smith and colleagues treated 33 patients with CIPN and found a significant reduction in pain persisting to 90 days (Figure 9) and dramatic improvement in how the pain interfered with normal life (Figure 10).⁴¹

[figure not shown]

Figure 9: Impact of Scrambler Therapy on neuropathic pain

[figure not shown]

Figure 10: "How much does pain interfere with walking?"

In this trial of 39 patients, Smith et al also saw significant improvements in both the motor and sensory subscales of the CIPN-20. (All p values < 0.001) Again, this was a single arm trial with no sham or placebo group.

[figure not shown]

Figure 11: Reduction in sensory symptoms

[figure not shown]

Figure 12: Reduction in motor symptoms

While these results in CIPN are promising, there are NO sham or placebo controlled trials. The results to date could potentially be due to placebo effect, as seen in one small trial of high frequency spinal cord stimulation⁴², but typical placebo CIPN effects are only about 10% pain relief over 3 months⁸⁻¹⁵. In the recent successful trial of duloxetine for CIPN¹⁶, the CIPN placebo group had reduced pain scores of only 0.1-0.2 points (on a 10-point scale) over 6 weeks, whereas the Scrambler Therapy 2-4 point drop happened within 10 days. Another alternative explanation is that the CIPN resolves over time, but the 10 day time period of treatment is likely to be too short for CIPN to resolve. We need sham or placebo-controlled trials to ensure that the treatment actually works, and if it works, the duration of effect.

While several hundred thousand CIPN patients stand to benefit, the bigger group of beneficiaries is the 116 million Americans with chronic pain⁴³. Evaluating if Scrambler Therapy works in one well-defined pain group will stimulate the needed research with other pain patients.

6. Patient Population

